Participants will be given a "covid-19 travel bag" which will include one 4 oz bottle of hand sanitizer (minimum 60% alcohol), 3 KN95 masks, and several alcohol wipes. We will ask the participants to do the following while traveling:

- Before walking into the airport: put KN95 mask on, this will stay on the entire duration of airplane travel
- When seated on airplane use alcohol wipes to disinfect all touch surfaces by the seat including the lap tray, buckle, arm rests, overhead light/air controls, and if in window seat, the window screen pull. Then, use hand sanitizer to clean hands.
- After exiting the airport in Colorado trash the first KN95 mask and replace with a fresh one, this mask will be used for the duration of the bus ride to Leadville or Breckenridge. Use hand sanitizer.
- When seated in the bus, use alcohol wipes to disinfect all touch surfaces by the seat. Use hand sanitizer.
- Upon arrival to Leadville or Breckenridge, trash the bus KN95 and replace with a fresh mask. Use hand sanitizer.
- Participants will be given a new "covid-19 travel bag" when they depart from Colorado so that their travel back may be as safe as possible. They will be expected to follow the same protocol for traveling to Eugene as they did while traveling to Colorado.

COVID testing protocol

If at any time during a subject's stay in Colorado they experience symptoms of COVID, they will be given a COVID test and their pod will be quarantined.

Safety Equipment available in the Cardiopulmonary and Respiratory Physiology Laboratory (where all testing and screening will be performed): Phillips FRx AED, a spare AED battery, and spare AED pads, bottled oxygen and face masks, all necessary equipment to run ACLS algorithms (suction, masks, breathing bag, etc.) and ACLS drugs such as chewable aspirin, and oxygen will be administered as required by AHA and ACLS guidelines. Additionally, a standard first aid kit is also available.

Emergency Procedures: According to American Heart guidelines, in the event of an adverse cardiopulmonary event, we will begin CPR, call 911 (as directed by U of O EH&S), and will continue CPR as required until emergency medical personnel arrive. Epinephrine auto-injectors (Epi Pens) will be available if the PI and colleagues judgement and/or 911 operator supported a decision to use an Epi Pen. In addition, a separate emergency procedure document is included.

Safety Monitoring: *Subjects will be given clear instructions that they should notify the investigators immediately if they experience any of the above-mentioned risk symptoms.* During the VO₂max test and recovery procedures, all subjects will be non-invasively and continuously monitored for vital signs using a forehead monitor to monitor arterial oxygen saturation and heart rate. During all other procedures subjects will be visually monitored for any signs of discomfort, distress or problems. During both exercise and resting procedures, the investigators will continuously ask the subjects how they are feeling and how they are doing. If subjects have ingested a core temperature pill they will be given an orange safety bracelet (no MRI) to wear until the study staff can ensure the pill has been passed.

Medical Monitor: [name], MD, University of Colorado, Colorado Springs (UCCS) will serve as the medical monitor for this study. [name] will receive regular reports on volunteer status. He will also evaluate adverse event reports and monitor study progress. He will discuss research progress with the PI on a weekly basis. He will promptly report discrepancies or problems to the IRB of record and the HRPO. He shall have the authority to stop this research study in progress, remove individual subjects from a study, and take whatever steps are necessary to protect the safety and wellbeing of research subjects until the IRB can assess their report. The medical monitor is required to review all unanticipated problems involving risk to subjects or others, serious adverse events and all subject deaths associated with the protocol and provide an unbiased written report of the event. At a minimum, the medical monitor will comment on the outcomes of the event or problem and in case of a serious adverse event or death, comment on the relationship of the event to participation in the study. The medical monitor will also indicate whether he concurs with the details of the report provided by the PI. Reports for events determined by either the PI or medical monitor to be possibly or definitely related to participation and reports of events resulting in death will be promptly forwarded to the USAMRMC ORP HRPO.

H. Potential Benefits of the Research

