Overview: The initial components of the study will be performed over 6 days at baseline to 1) screen subjects for inclusion in the study and 2) obtain baseline measurements, with all studies conducted at the Cardiopulmonary Lab, Eugene, OR. These screening and baseline studies will be followed by 4 weeks of placebo or drug interventions (Cardiopulmonary Lab, Eugene, OR) and 14 days living at high altitude (Breckenridge or Leadville, CO). Within 1 week after returning to Eugene, OR, post-altitude measures will be made. Refer to Figure 1 below for a schematic representation of the timing and location of measurements. Each subject, regardless of intervention arm, will perform all protocols described below. All screening in Eugene, OR is scheduled for 6 days, but screening could take up to 10 days in the case of equipment malfunction or if the subject prefers to spread tests out over additional days.

* Indicates protocol that will be done on either day listed in early or mid altitude measures

What follows is a detailed description of each study day:

BASELINE: EUGENE, OR RESEARCH SITE

All studies done in Eugene will be done in either laboratory space within Pacific Hall and/or on running tracks and trails within the Eugene/Springfield metropolitan area or very close to this community.

Any subject with childbearing potential will be required to take a pregnancy test on VO₂max days and Hemoglobin mass testing days (both at baseline and altitude) as the other testing days will not involve any activity that would otherwise affect the fetus.

Day 1 – Informed consent, medical History, blood draw: Cardiopulmonary Lab, Eugene, OR (~60 min)

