Subjects who express interest in the study will have any initial questions answered on the phone or over email, depending on subject preference. Those interested in continuing with the study will arrive to the lab, and subjects will undergo informed consent and complete a self-report health history questionnaire, and complete a menstrual cycle history questionnaire (biological women only) (~30 min). Subjects will have the option to undergo informed consent remotely prior to arriving to the lab (see 'Informed Consent Process' below) but will complete all other paperwork, including signing the informed consent, upon arrival to the lab. Menstrual cycle history will be documented for control purposes for blood biomarker analysis, although subjects will not be required to be in a certain phase for testing, nor will they be excluded for contraceptive use.

After completing paperwork, subjects will undergo physical examinations by either a Nurse Practitioner or Physician Assistant 25 mL blood draw for iron, ferritin, transferrin, basic metabolic panel, and complete blood count measurements to be analyzed by QUEST. Subjects will be asked to either give or deny permission to the [name] Lab to re-contact them after the end of the study. Lastly, subjects will be asked to use an online Qualtrics survey, which will be emailed to every consenting subject, to log daily exercise activity for the duration of the study. (~30 min).

Day 2 – Army Physical Fitness Tests (APFTs): Cardiopulmonary Lab, Eugene, OR (~60 min)

Subjects will perform a modified version of the Army Physical Fitness Tests (APFTs) outdoors at the University of Oregon. The APFT will include 2 minutes of push-ups and sit-ups and a 5k run. Total time ~1 hour.

Day 3 – Lung function, cardiac screening, blood draw, Acute Mountain Sickness (AMS) questionnaire with finger saturation, and cognitive function testing: Cardiopulmonary Lab, Eugene, OR (~125 min)

Subjects will perform pulmonary function testing (~15 minutes) and cognitive function testing (~20 minutes).

Subjects will have an intravenous catheter (IV) placed. Subjects will then undergo comprehensive ultrasound screening. Amount of blood flow travelling through the PFO/ASD and IPAVA will be graded using saline contrast echocardiography while the subject is breathing room air. Pulmonary artery pressure, cardiac output, and TAPSE will also be measured using ultrasound (~60 minutes).

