Subjects will complete the Lake Louise Questionnaire (LLQ) and Environmental Symptoms Questionnaire (ESQ) to determine acute mountain sickness (AMS). Subjects will be instrumented with a pulse oximeter to measure oxygen saturation (~15 minutes).

Lastly, subjects will have resting ventilation and HCVR measured (~15 minutes).

Day 4 – VO₂max testing day: Cardiopulmonary Lab, Eugene, OR (~30 min)

Subjects will perform a VO₂max test (~30 minutes). Additionally, resting, exercise, and post-exercise heart rate and systemic blood pressure will be measured. Any subject with child bearing potential will be required to take a pregnancy test prior to the VO₂max test.

All subjects will arrive at the Cardiopulmonary lab and will be given a telemetric core temperature pill to take 5-10 hours before arriving for **Day 5** testing. If subjects do not take the pill the night prior to exercise testing, they will have to take the temperature pill as a suppository the morning of testing.

To take the core temperature pills, subjects will be told to swallow with a glass of water or other beverage. There are no restrictions for fluid or food consumption after the pill has been ingested and subjects will be told not to chew the telemetric pill. In order to insert the pill as a suppository, subjects will be instructed to insert the pill past the first digit of your finger and given lubricant and a glove to assist with the insertion process. Research staff will be available to give additional information about the insertion process if subjects have more questions. These directions apply to every time subjects take the core temperature pills.

Day 5 – Performance Stabilization, Eugene, OR (occurs ~30 days before departure for Colorado) (~30 min)

To further ensure accurate baseline measurements of physical performance, the top 80 subjects (and 20 alternates) with the most similar physical characteristics will repeat the 5K. This strategy will minimize the influence of learning effects associated with the tests and facilitate matching between groups. (~30 min).

Day 6 – Hemoglobin mass, Eugene, OR (occurs ~30 days before departure for Colorado) (~75 min)

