Intravenous catheter and venous blood draw: We will place a 20-22 gauge (small diameter) IV into a vein in the subject's arm. This IV will be used to for various tests – blood draws for Hb mass & p50, blood draws to measure various biomarkers in the blood, iron/saline infusion during drug treatment, and for contrast bubble injections during ultrasound measures at sea level.

Venous blood draw: Blood for measuring biomarkers will be drawn from an IV (60 mL per blood draw) and centrifuged, and de-identified plasma and serum stored at -80°C until assayed. Additionally, blood will be drawn for baseline iron, transferrin, ferritin, complete blood count, and basic metabolic panel analysis (via QUEST diagnostics, 25 mL) on baseline day 1, and blood will be drawn for sickle cell screening on baseline day 6 (via QUEST diagnostics, 5 mL). Intravenous blood for biomarker analysis will be drawn on baseline 6, and on the second day of iron or saline infusion

to minimize the number of needle sticks. Blood will also be drawn days 1, 7, and 13 at high altitude, and at sea-level post altitude. 60 mL of blood will be drawn for biomarker analysis on each of these blood draw days.

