Those with inability to be headache-free when consuming the amount of caffeine in two six-ounce cups of coffee or less per day.

Extended exposure (>6 hours) to high altitude above 1000m in the month leading up to departure to Colorado.

Those who have been on an airline flight over six hours (the lowered cabin pressure for an extended period of time approximates exposure to high altitude) within the month leading up to departure to Colorado.

Those who are unable to achieve the minimum physical criteria as outlined above.

Anyone with lung function below the lower limit of normal per GLI standards.

Previous diagnosis of high altitude pulmonary edema or high altitude cerebral edema upon altitude exposure.

Failure to get fully vaccinated against COVID-19. Choosing not to be vaccinated will result in exclusion.

Family history of clotting disorders, anemia or venous thrombosis.

Plans for professional competition during or within 1 week after participation in this study as participation may enhance your aerobic performance

Presence or absence of a PFO once we have enrolled a sufficient number of each group representation in the general population (e.g., ~40% of population has a PFO and ~60% does not). However, all subjects will be allowed to

complete all baseline screening to assure that we will have enough subjects to go to Colorado

Biological sex once we have enrolled a sufficient number of males and/or females as we are aiming to enroll ~50% of each sex. However, all subjects will be allowed to complete all baseline screening to assure that we will have enough subjects to go to Colorado.

Subjects will be excluded from telemetric pill ONLY if they have a history of obstructive diseases of the gastrointestinal tract including diverticulosis, diverticulitis, inflammatory bowel disease, peptic ulcer disease, Crohn's disease, ulcerative colitis, or previous GI surgery.

Detailed recruitment methods

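### Cycle information for the biomarker analysis is taken only on baseline Day 1, but five of the six biomarker draws come about 32–53 days later, so cycle phase at those draws could only be projected

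*Combined protocol and SAP*

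**What the plan says.** Section C, Day 1, has women complete a menstrual history questionnaire and gives its purpose: "Menstrual cycle history will be documented for control purposes for blood biomarker analysis". The same sentence leaves phase uncontrolled by design: "subjects will not be required to be in a certain phase for testing, nor will they be excluded for contraceptive use". No later visit in Section C lists any menstrual item. The online survey set up on Day 1 is there to "log daily exercise activity for the duration of the study", and the pregnancy tests do not date a cycle.

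The blood-volume table in Section G (Blood Removal) shows six 60 mL biomarker draws: baseline Day 6, post-treatment, altitude days 1, 7 and 13, and post-altitude. Section C, Venous blood draw, agrees on the last four: "Blood will also be drawn days 1, 7, and 13 at high altitude, and at sea-level post altitude".

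The content of the questionnaire is not given. The documents describe no model for the biomarkers and do not say how cycle history would enter one.

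**The concern.** The plan singles out the menstrual cycle as something to control in the biomarker analysis, and it neither schedules testing by phase nor restricts contraceptive use. The Day 1 history is therefore the only control left. It is recorded more than four weeks before most of the samples it is meant to help interpret, and those are all the post-dose, altitude and post-altitude samples.

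The exclusion criteria in Section D say "we are aiming to enroll ~50% of each sex", so about half the subjects are affected. Any variation in a marker that follows cycle phase would be only partly removable. The markers belong to Aim 2. Section A also wants them for describing natural acclimatization in the placebo group and for finding signs of illicit use of either compound. Onset dates not asked for at the time are hard to recover later.

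**Working it through.** **Timing.** The plan gives no figure for this interval, so it is built from the schedule, with Day 1 as day 0.

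- Section C, Overview: "All screening in Eugene, OR is scheduled for 6 days, but screening could take up to 10 days". Day 6 is therefore day 5 nominally, and up to day 9.
- Section C, Day 6: about 30 days before departure. Departure = 5 + 30 = 35, taken as altitude day 1 because testing starts on arrival.
- Second draw: Section C, Venous blood draw, puts it on the second infusion day (Wednesday before a Saturday departure, 35 − 3 = 32). The Drug intervention paragraph puts it after the last dose (from Friday, 35 − 1 = 34). These two statements need reconciling.
- Altitude days 7 and 13: 35 + 6 = 41 and 35 + 12 = 47.
- Post-altitude days 3–5: altitude day 14 is day 48, so 51–53.

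The draws fall on days 5, 32 or 34, 35, 41, 47 and 51–53. Other readings of the five later draws:

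- 10-day baseline: departure 9 + 30 = 39, range 36–57.
- 28 days from Day 6 to departure: departure 33, range 30–51.
- Day 6 on the day before the first tabulated dose: that dose is 24 days before departure, so Day 6 is 25 days before. Departure 30, range 27–48.

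**Projection error.** The inputs here are assumptions, not taken from the documents: mean cycle 28 days, luteal phase fixed at 14 days, no contraceptive use, and last onset and usual length known exactly on Day 1. Within-woman cycle-length SD is varied. Projected phase is luteal if (days since the onset known on Day 1) mod 28 is 14 or more. True phase comes from simulated cycles. Percentage of draws misplaced:

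| Days after Day 1 | SD 2 | SD 3 | SD 4 |
|---|---|---|---|
| 5 | 11 | 17 | 22 |
| 32 | 16 | 24 | 31 |
| 35 | 16 | 24 | 32 |
| 41 | 17 | 25 | 33 |
| 47 | 18 | 27 | 35 |
| 51 | 18 | 27 | 35 |

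Day 53 is within about half a point of day 51. Guessing would misplace 50%.

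**If onset is asked at each draw.** A draw is misplaced only when it falls between day 14 of the cycle and the true start of the luteal phase. That gap is |L − 28| days in a cycle of length L. The misplaced share is E|L − 28| / 28 = SD × √(2/π) / 28:

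- SD 2: 1.60 / 28 = 5.7%
- SD 3: 2.39 / 28 = 8.5%
- SD 4: 3.19 / 28 = 11.4%

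Simulation gives the same values.

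**What this does to adjustment.** With phases about equally common and symmetric errors, a misplaced share m shrinks the observed phase difference by the factor 1 − 2m. The share of phase-related variance that adjustment removes is (1 − 2m)².

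- Projected from Day 1, m = 0.16 to 0.35: factor 0.68 to 0.30; variance removed 46% to 9%.
- Asked at each draw, m = 0.06 to 0.11: factor 0.88 to 0.78; variance removed 77% to 61%.

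**Women per arm.** Section C, Day 5, takes 80 subjects forward, with 20 alternates. Three arms, assumed equal, with half women: 80 / 3 × 0.5 ≈ 13.

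**The case against.** The plan promises control by cycle history; it does not promise phase at each draw. History could mean regularity, absence of periods or contraceptive use, and a single questionnaire can supply those. That is a fair reading, and with the questionnaire unseen it cannot be excluded. But regularity does not locate a sample within a cycle, and nothing in the plan updates contraceptive use after Day 1.

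A reader might go further and infer that phase cannot be placed at all, or that the control fails for every post-dose sample. The figures above do not support that: if the Day 1 form records last onset and usual length, about 65–84% of the later draws are still placed correctly. The error is also not only a matter of delay, since projection already misplaces 11–22% at Day 6.

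A reader might also infer bias in the drug comparisons. The documents do not support that either. Section C, Drug intervention, describes randomization with a concurrent placebo and one visit schedule for all arms, so unmeasured phase is mainly noise, and chance imbalance is part of ordinary random error.

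Two further objections stand. The misplacement rates apply only to naturally cycling women, whose share is unknown because contraceptive users are admitted. And no phase effect on any listed marker is given, so a material loss of precision is not shown. Stored serum could in principle be assayed for sex hormones, but none is named in the open-ended marker list under Blood measures.

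**Conclusion.** The point holds as a minor, inexpensive improvement, not as a contradiction or a demonstrated threat to an aim. The cycle information meant to support the biomarker analysis is collected once, about 32–53 days before five of the six draws on the nominal calendar and about 27–57 days across the readings considered. For naturally cycling women, projecting phase from Day 1 would misplace about 16–35% of those draws, against about 6–11% with onset asked at the draw. Both ranges rest on the assumed 28-day mean, 14-day luteal phase and SD of 2–4 days; greater irregularity worsens both.

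The consequence is added noise in arm contrasts among about 13 women per arm, and less interpretable within-person change and placebo-group description, which randomization between arms does not protect. How much this matters for any one marker cannot be determined from the documents.

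**What to change.** At each of the six biomarker draws, record the date of onset of the last menses and current hormonal contraceptive use. The daily exercise log, which runs throughout the study, and the daily compliance survey in Colorado (Section G, COVID Compliance protocol) can carry the questions. State in the analysis plan that phase or contraceptive status at the draw, rather than the Day 1 history alone, is the covariate in the biomarker models for women.

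The cost is a short survey item at six existing visits, with no new procedure, sample or staff. The downside is a small added burden for participants. It should be in place before the first baseline Day 6 draw, because missing onset dates cannot be dependably reconstructed afterwards.

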Subjects will perform hemoglobin mass (Hb mass) and p50 measures (~75 minutes). This measurement involves placing an IV and drawing an additional 10 mL of venous blood. Any subject with child bearing potential will be required to take a pregnancy test prior to Hb mass testing. In addition, subjects will have baseline venous blood drawn (60 mL of venous blood will be analyzed for various biomarkers and 5 mL for sickle cell screening to be analyzed by QUEST). Dried Blood Spot samples will be taken utilizing a commercially available dried blood spot sampling device (80 uL) (TASSO, Tasso Inc, Seattle, USA). Dried blood will be analyzed for HGB, CD71/Band3, ESAs, and reticulocytes. Total Blood drawn for this day of ~76 mL.

Drug intervention, Eugene, OR

For the 4 weeks immediately prior to the scheduled departure date, subjects will arrive at the Cardiopulmonary Lab as required by their intervention schedule (see 'Drug Intervention' below for details) to receive their assigned intervention via a sub-cutaneous injection and/or intravenous

injection. After the last dose, subjects will have venous blood drawn (~60 mL) prior to departure to Colorado for measurements of various biomarkers. A dried blood drop sample (80 uL) will also be taken.

COLORADO FIELD SITE:

All studies performed in Colorado will happen in laboratory space created by the investigators and/or on running tracks and trails in or very near Leadville or Breckenridge, CO.

Early high-altitude measures: Days 1-3

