We will study civilians who are recreational athletes who meet the basic health and physical fitness eligibility standards as evaluated using the modified Army Physical Fitness Test (APFT). We use the APFT because of its standard of use across all US Armed Forces, and our experience with it successfully selecting broadly fit students, i.e. a specialized runner might struggle, but a male or female with overall high aerobic fitness and strength will do well. Subjects will be matched and assigned to either the placebo or the two intervention groups to achieve the necessary statistical power to detect meaningful changes in health and performance at high altitude. Our team has extensive experience in recruiting and screening subjects on college campuses to achieve this goal (4-64).

Up to 300 volunteers will be screened in Eugene, Oregon to identify 100 subjects meeting the inclusion and exclusion criteria (see below).

Inclusion criteria	Exclusion criteria
Ages 18 to 40	Smokers
Recreational athletes able to pass the APFTs	Previous severe COVID infection or contraction of any COVID infection occurring during the study. Previous mild to moderate COVID infections will be considered for the study on a case-by-case basis as determined safe by clinical research staff (see inclusion criteria).
Men and women of any ethnic background	
Medical and dental insurance	
Able to read and speak English	Carboxyhemoglobin values (HbCO) 3% or greater at baseline
Fully vaccinated against COVID-19	
*If a subject is taking medication that is deemed safe and will not interfere with the main outcome measurements of the study as determined by clinical research staff, they will be included.	Diseases or disorders known to be affected by hypoxia or the drugs used in this study, including but not limited to hypotension, anemia, sickle cell trait or disease, and diabetes.
*If a subject had a previous mild to moderate COVID-19 infection but is deemed safe for all research activities by clinical research staff, then they will be included in the study.	Anyone unable to receive the investigational drugs used in this protocol (EPO or iron). Those with a history of significant head injury, migraines or seizures. Anyone that is pregnant or trying to become pregnant.

Any medication determined by the clinical research staff to be unsafe or to interfere with the outcome measurements of the study.

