minimize these risks, all precautions and warning labels will be followed, and dosing volumes will be strictly adhered to. Serious [allergic reactions](#) to this drug are unlikely, but may include: [rash](#), [itching/swelling](#) (especially of the face/[tongue](#)/throat), severe dizziness, [trouble breathing](#). Subjects will be excluded from the study for any health problems that may negatively effect their reaction to these drugs (see table of inclusion and exclusion criteria and drug appendices for specific exclusion criteria). FDA recall lists for drugs being administered to participants will be checked weekly beginning with the initiation of drug administration.

Risks for subjects who are pregnant: Potential risks to subjects who are pregnant (beyond the risks outlined above for the general population) include exercising beyond than what is recommended by their doctor (see 'VO_{2max} testing' and 'additional exercise testing' above) and potential unknown risks to the child bearer or fetus from carbon monoxide inhalation (see 'Hb mass measurement' above). None of the additional risks described above are greater in those who are pregnant. Due to the increased risk of exercise testing and Hb mass measurements, any subject with childbearing potential will be required to take a pregnancy test on a day that involves maximal exercise testing (VO_{2max}) and Hb mass testing while at baseline and in Colorado, and if such a test comes back positive, they will be immediately excluded from the study. Therefore, there is no added risk to the child bearer or the fetus from any of the above-mentioned protocols, as they will not undergo those procedures. As such, the probability of an adverse reaction is zero, and the severity of an adverse reaction is zero.

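### Sickle cell status is an exclusion, but its only laboratory test is drawn at the same visit as duplicate carbon monoxide rebreathing, so the result cannot precede the gas

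*Combined protocol and SAP*

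**What the plan says.** **The exclusion.** The table in section D rules out disorders known to be affected by hypoxia or by the study drugs, "including but not limited to hypotension, anemia, sickle cell trait or disease, and diabetes".

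**The test.** The Day 6 text in section C reads "60 mL of venous blood will be analyzed for various biomarkers and 5 mL for sickle cell screening to be analyzed by QUEST". The venous blood draw procedure in section C agrees: "blood will be drawn for sickle cell screening on baseline day 6 (via QUEST diagnostics, 5 mL". So does the volume table under Blood Removal in section G, which shows 5 mL of screening blood at baseline 6. The Day 1 draw covers iron, ferritin, transferrin, a metabolic panel and "complete blood count measurements to be analyzed by QUEST". It has no sickle test.

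**The same visit.** The Hb mass procedure in section C places two CO rebreathing tests on baseline Day 6. Each dose is expected to raise carboxyhemoglobin (HbCO) by about 6% to 8%. Section G expects about 15% after both.

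**What must be known before CO.** A pregnancy test is required before Hb mass testing, and a high baseline HbCO (3% or greater) excludes. No sentence requires the sickle result before CO or before the first infusion.

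**Order of phases.** The Overview in section C says "These screening and baseline studies will be followed by 4 weeks of placebo or drug interventions". It also allows that "screening could take up to 10 days in the case of equipment malfunction".

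**The concern.** The plan treats sickle status as disqualifying and pays for a laboratory test, so it does not rely on self-report alone. But a sample sent out on Day 6 cannot return a result in time for a procedure done on Day 6. A carrier who does not know their status would therefore complete both CO exposures before the exclusion could apply.

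The plan already makes CO conditional on two other results, pregnancy and baseline HbCO. The sickle result is the one eligibility blood test that its timing keeps from serving the same purpose. What is at stake is whether one exclusion can work before one procedure.

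**Working it through.** No power or sample size figure bears on this. The check is of order, intervals and volumes. Days 1 to 6 are visit labels, so the intervals below are approximate.

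**1. Sample to CO, as scheduled.** Both fall on Day 6: 6 − 6 = 0 days. This needs no assumption about laboratory turnaround.

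**2. Sample to first infusion, as scheduled.** Day 6 is about 30 days before departure (Day 6 heading).
- By the iron text, the first infusion is 4 weeks before travel, or 28 days: 30 − 28 = 2 days.
- By the intervention calendar, it is the Wednesday of the first row, with departure on the Saturday three weeks later: 3 × 7 + 3 = 24 days before departure, so 30 − 24 = 6 days.

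The margin is about 2 to 6 days. Turnaround is not stated.

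**3. Intervals with an earlier draw, if screening takes 6 to 10 days.**

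| Draw | Before CO | Before first infusion |
|---|---|---|
| Day 6 (now) | 0 | 2 to 6 |
| Day 3 | 6 − 3 = 3 to 10 − 3 = 7 | 3 + 2 = 5 to 7 + 6 = 13 |
| Day 1 | 6 − 1 = 5 to 10 − 1 = 9 | 5 + 2 = 7 to 9 + 6 = 15 |

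The intervals are longer if the visits are spread further apart.

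**4. Possible delay to Day 6.** Assume a turnaround T of 1 to 7 days (not in the documents) and the shortest, six-day schedule.
- Day 1 draw: max(0, T − 5) = 0 to 2 days.
- Day 3 draw: max(0, T − 3) = 0 to 4 days, which could exceed the shorter 2-day margin in step 2.

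**5. Size of the CO exposure.** With baseline HbCO of 1.5% to 2.0% and two doses of 6% to 8%: 1.5 + 2 × 6 = 13.5% to 2.0 + 2 × 8 = 18%. This agrees with the plan's figure of about 15%.

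**6. Blood volumes.** The plan's own figures come first.
- Day 6 now: 60 + 5 + 10 + 0.08 = 75.08 mL (plan: about 76).
- Before departure now: 25 (Day 1) + 2 (Day 3 p50) + 75.08 (Day 6) + 60.08 (post-treatment) = 162.16 mL (plan: about 162).
- Day 6 without the sickle tube: 70.08 mL, the same make-up as the altitude days that the plan calls about 71 mL.
- Day 1 becomes 25 + 5 = 30 mL, or Day 3 becomes 2 + 5 = 7 mL. The pre-departure total stays at 162.16 mL.

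**7. Extra assays.** Up to 300 people are screened, and 80 plus 20 alternates are selected for the Day 5 repeat run. If Day 6 is confined to those 100, a Day 1 draw adds at most 300 − 100 = 200 assays. If more than 100 people reach Day 6, it adds fewer.

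**The case against.** **The exclusion is tied to hypoxia and the study drugs, and the test precedes both.** This stands. The documents state no sickle-specific risk from CO or from exercise. CO rebreathing also has safeguards: subjects breathe 100% oxygen beforehand, the circuit is filled with oxygen, oxygen is given if HbCO reaches 20%, and section G reports no ill effects across varied populations. These limit the weight of the point but do not change the order. A test listed as a screening panel still cannot screen for a procedure at its own visit.

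**Other screens come earlier.** The recruitment script, Day 1 health history, blood count and family-history exclusion for anemia may identify some carriers. None is a sickle test, and a carrier unaware of their status could pass them all.

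**Late testing saves money.** Testing only after selection is ordinary staged screening, and it is a fair reason for the present order. The saving is at most about 200 assays.

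Three stronger readings are tempting but not supported:
- *A carrier would receive study drug or travel to altitude.* The Overview puts screening before dosing, section D describes volunteers "screened in Eugene, Oregon to identify 100 subjects meeting the inclusion and exclusion criteria", and section G adds: "Subjects will be excluded from the study for any health problems that may negatively effect their reaction to these drugs". These imply that eligibility is settled first. For dosing, the only point is that the margin is short, turnaround is unstated and no rule requires the result.
- *The order exposes carriers to three hard exercise tests.* The Day 2 5K, the VO2max test and, for those selected, the repeat 5K do come before Day 6. But no sickle-specific exercise risk is stated, and the Day 2 run would probably still precede the result after a Day 1 draw.
- *The randomised comparison is biased.* The sample is taken at a baseline visit before any dosing, on the same schedule for every arm.

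**Conclusion.** The concern holds as a minor point of subject safety. As scheduled, the sickle exclusion cannot act before duplicate CO rebreathing in a carrier unaware of their status, because sample and procedure share a visit. That rests on the documents alone. Whether the result would be back before the first infusion depends on a turnaround that the documents do not give.

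The documents give neither the prevalence of the trait nor the share of carriers who are unaware, so no number of affected subjects and no harm rate is offered. The fix firmly protects CO rebreathing and makes the check before dosing explicit. A result that also arrives before the VO2max test or the repeat 5K is an incidental gain. The delay figures rest on the assumed turnaround of 1 to 7 days.

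**What to change.** Move the 5 mL sickle sample to the Day 1 QUEST draw, or to the Day 3 IV, which already supplies the p50 sample. Add one sentence: a negative sickle result is required before any CO rebreathing and before the first study infusion, and Day 6 moves if the result is late. Update the Day 1 or Day 3 text, the Day 6 text, the venous blood draw procedure and the Blood Removal figures and table. The stated daily maximum falls from about 76 to about 71 mL.

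The cost is modest. There is no extra needle stick, and no extra blood for anyone who reaches Day 6. People who leave between the new draw and Day 6 give 5 mL more. A Day 3 draw needs no more assays than a Day 1 draw, and fewer if anyone leaves in between, but it leaves less time for the result. The remaining cost is the possible short delay to Day 6 shown above.
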